### 3 INVESTIGATIONAL PLAN

#### 3.1 STUDY DESIGN

This is a prospective, multicenter, multinational, open-label, randomized, two-arm, comparative phase 3 study. Approximately 35 sites in the US, Europe and Israel are planned for the study. Subjects who continue to meet inclusion and exclusion criteria on the day of surgery will be randomized in a 1:1 ratio to receive either the HAV or the ePTFE graft during surgery. The randomization will use a block size of 4 subjects and will be stratified by the upper arm or forearm placement. Subjects are considered enrolled at the time of completed informed consent. At least 350 subjects with implanted study conduits [175 with Human Acellular Vessel (HAV), 175 with an expanded polytetrafluoroethylene graft (ePTFE)] are planned to be enrolled in the study.

All enrolled subjects will be followed by study specific visits until the subject completes 2 years (24 months) of follow-up after implantation (irrespective of patency status).

After 2 years, only subjects with a patent conduit will continue to be followed (while the study conduit remains patent) for up to 5 years (60 months) post-implantation or until conduit abandonment (loss of Secondary Patency) at routine study visits. The expected duration of the clinical investigation is 76 months from the initiation of enrollment through the completion of data collection. See Appendix 1 of the study protocol for details of the schedule assessments.

A Data Monitoring Committee (DMC) will be established to review safety on an ongoing basis and to provide recommendations about stopping, continuing or otherwise modifying the study. The DMC will review data unblinded by treatment group and will consist of individuals who are not directly involved in the conduct of the study. As part of their oversight of study conduct, the DMC will review the pattern of interventions and abandonments between treatment groups overall and by study site to assess whether the management of access complications is similar in the two treatment groups.

A separate charter will be established that will describe the roles and responsibilities of the DMC. Responsibilities of the DMC will include review of aggregate safety data from other studies in the HAV clinical development program.

## 3.2 TREATMENT

This study compares a 6 mm diameter ePTFE graft (Gore® PROPATEN® Vascular Graft or Bard® Impra® Vascular Graft) with the Humacyte Human Acellular Vessel (HAV) in their use as conduits for vascular access. Selection of the ePTFE graft to be implanted in a subject randomized to the comparator arm will be made by the investigator from the two protocol-specified options.

### 3.2.1 Treatment Arm Assignment

At least 350 subjects who meet inclusion/exclusion criteria will be randomized in the study across multiple investigative sites. Study site personnel will randomize the subject utilizing a voice- or web-based randomization system to either HAV or ePTFE during surgery (i.e., after the surgical site [upper- vs fore-arm] has been selected and after confirmation that the subject is not a candidate for creation of an autologous AV fistula). Randomization may only occur once the arterial and venous exposures have been completed with confirmation of adequate arterial inflow and venous outflow. The randomization schema will ensure that subjects will be randomly assigned in a 1:1 ratio to the HAV or ePTFE arms of the study.

The randomization will be stratified by country (6 planned: US, Poland, Israel, Germany, UK and Portugal) and the upper arm or forearm placement based on the Investigator's determination of where the study conduit should be located. A blocked randomization of size 4 will be used. Subjects are considered enrolled at the time of completed informed consent. Country will not be included as a stratification variable for the statistical analysis for effect, but is only included in the randomization scheme to ensure a balance of treatment groups in each country.

### Controlling against bias

This is an open-label, comparative study. It is not possible to blind the investigators or study subjects. Study endpoints will be determined by the clinical decisions of the investigators (except for study conduit revisions and access-related infections). To reduce the potential for bias a Clinical Events Committee (CEC) will:

- Prospectively provide to study sites a set of clinical guidelines for study conduit interventions and abandonment.
- Review individual study conduit interventions and abandonment in a blinded fashion to assess compliance with these guidelines.

- Adjudicate study conduit revisions to determine whether the original study conduit was still being used for dialysis.
- Adjudicate access-related infections using the Centers for Disease Control and Prevention (CDC) definitions for dialysis-associated infections (CDC 2013).

The outcome of these adjudications (i.e., those involving study conduit revisions and access-related infections) will be used as endpoints in the trial rather than the investigator determinations. All other study endpoints will be based on the clinical decisions of the investigators.

Additionally, cumulative event rates overall and by study arm will not be available to staff involved in the management of the study or study subject care.

### **Subject Compliance with IMP**

Not Applicable

## **4 GENERAL CONSIDERATIONS FOR DATA ANALYSIS**

Statistical analysis of data from this study will be the responsibility of CTI Clinical Trial & Consulting Services. Any change to the data analysis methods described in the protocol will require an amendment of this SAP only if it changes a principal feature of the protocol. Any other change to the data analysis methods that are described in the protocol, and the justification for making the change, will be described in the clinical study report. Additional exploratory analyses of the data will be conducted as deemed appropriate.

Summaries and analyses will be performed by CTI Clinical Trial & Consulting Services and/or by Humacyte. Validated results will be reviewed by statisticians and clinicians at Humacyte for approval. For both safety and efficacy analyses, all analyses will be performed by treatment group (HAV, ePTFE graft). Subject listings of all data from the case report forms (CRFs) as well as any derived variables will be presented.

All analyses will be implemented using SAS Version 9.2 or more recent version.

The analyses for this study will be performed as follows:

- The primary analysis will be performed after all subjects are at least 18 months post-implantation and have completed the 18-month visit or have been censored for death, kidney transplant or withdrawal.
- A second analysis will be performed after all subjects are at least 24 months (2 years) post-implantation and have completed the 24-month visit or have been censored for death, kidney transplant or withdrawal.

- A final analysis will be performed after all subjects with a patent conduit at 2 years (24 months) have completed 5 years (60 months) of follow-up after implantation, or until conduit abandonment, if earlier.
- Additional ad hoc analyses may be performed as needed after the 24 month analyses.
- Interim safety and efficacy data will be provided periodically to the DMC as per the DMC Charter.

A hard database lock will be required for the data included in the planned primary (18 month) and second (24 month) analyses. Additional soft database locks may occur to support DMC activities. A final hard lock will be required for the final analysis.

Unless otherwise specified, continuous variables will be summarized by presenting the number of non-missing observations, mean, standard deviation, median, inter-quartile range, minimum and maximum. Categorical variables will be summarized by presenting the number of subjects and percentage for each category.

Unless otherwise noted, all tests of treatment effects will be conducted at a 2-sided alpha level of 0.05 and two-sided 95% confidence intervals (CI) will be calculated. All tests of interactions between treatment groups and other factors will be conducted at a 2-sided alpha level of 0.10, unless otherwise noted. Parametric and nonparametric methods, as determined by the distribution of each variable, will be used to test statistical hypotheses of continuous variables. In the event of highly skewed data, a logarithmic transformation will be considered prior to any statistical testing.

All p-values will be rounded to 3 decimal places. A p-value rounded to 1.000 will be displayed as >0.999, and a p-value rounded to 0.000 will be displayed as <0.001.

Multiplicity will be managed by testing the primary and key secondary endpoints in a hierarchical fashion. All analyses will be performed using data pooled across sites.

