3.2 Secondary Objectives

3.2.1 Key Secondary Objectives:

Efficacy

To compare the Primary Patency of the HAV with that of the ePTFE graft.

Safety

To compare the rate of access-related infections for the HAV with that of the ePTFE graft.

3.2.2 Other Secondary Objectives:

Efficacy

1. To compare the rate of interventions needed to maintain/restore patency of the HAV with that of the ePTFE graft.
2. To compare the Primary Assisted Patency of the HAV with that of the ePTFE graft.
3. To describe the histopathological remodeling of samples from HAV and ePTFE grafts.
4. To compare the efficiency of dialysis with the HAV with that of the ePTFE graft in a subset of subjects.

Safety

1. To compare the safety and tolerability of the HAV with that of the ePTFE.
2. To compare the relative rates of true aneurysm and pseudo-aneurysm formation.

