#### 2.2.0.3 ***Key Secondary Safety Endpoint***

Access-related infections ([CDC 2013](#)).

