#### **4.5 MULTIPLE COMPARISONS**

Multiplicity for the primary and key secondary endpoints will be managed through a series of hypotheses presented in Section 6.2.

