## 6.2 SECONDARY EFFICACY ENDPOINTS AND ANALYSES

If the primary efficacy analysis demonstrates non-inferiority, the following key secondary efficacy analyses will be performed at the same timepoint in the ITT analysis set using a fixed sequence testing procedure to control the overall level of significance. Thus, the results of a given key secondary analysis will be considered confirmatory only if the results of all previous tests are successful based on the use of a two-sided test at the alpha=0.05 level of significance. However, once a non-successful result is obtained, all subsequent results will be considered as exploratory rather than confirmatory. The key secondary analyses are the following:

- Superiority analysis of the time to loss of Secondary Patency using the same statistical approach as specified for the primary analysis, except that a two-sided superiority test will be performed,
- Non-inferiority analysis of the time to loss of Primary Patency using the same statistical approach and non-inferiority margin as specified for the primary analysis, and
- Superiority analysis of the time to loss of Primary Patency using the same statistical approach as specified for the primary analysis, except that a two-sided superiority test will be performed.

In order to provide descriptive summary statistics that are of interest, point estimates and 95% confidence intervals for patency (Primary, Primary Assisted and Secondary) survival probabilities will be provided for each group at 6, 12, 18, and 24 months. These estimates will be computed from Kaplan-Meier survival curves for each treatment group for each of the endpoints. For subjects who discontinue early or who complete without meeting criteria for the event, the time-to-event will be censored and defined as the number of days from randomization to the subject's last visit during the study.

Other secondary endpoints to be analyzed include:

- Interventions required that successfully achieved/maintained Secondary Patency. Interventions include whatever is done at one session. For example, thrombectomy + angioplasty at one session would be considered as 1 intervention. Summaries will include:
  - Proportion of subjects who had at least one intervention
  - Number of interventions per subject
  - Distribution of how many had 1, 2, 3... interventions

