### **Access-Related Infections**

In addition to the summaries indicated above in Section 7.2.4, the following access-related infection outputs are planned:

- Rate of access-related infections per 100 person-years of HAV/ePTFE graft use (i.e. censored at abandonment)
- Rate of access-related infections per 100 person-years over the 2-year post-implantation follow-up period

The analysis of access-related infections will be based on adjudicated events using a standardized definition of access-related infections. The infection rates will be compared using a Poisson regression model with treatment group and the surgical placement stratification variable as factors, if no overdispersion is present. Otherwise, a negative binomial regression will be used to adjust for overdispersion. The analysis will be conducted using a two-sided test at the alpha=0.05 level of significance. The following aspects associated with access-related infections will be described and summarized:

- The timing of first study access-related infection relative to the initiation of dialysis using the implanted conduit
- The use of intravenous antibiotics
- The need for hospitalization
- Other potential factors identified by the CEC

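### SAP 4 and 4.5 claim hierarchical control for all key secondary endpoints, but access-related infection is tested outside the hierarchy, under two rate definitions, each at two-sided 0.05

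*SAP*

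**What the plan says.** Two summary statements in the SAP describe the multiplicity strategy, and neither is limited to efficacy. Section 4: "Multiplicity will be managed by testing the primary and key secondary endpoints in a hierarchical fashion". Section 4.5: "Multiplicity for the primary and key secondary endpoints will be managed through a series of hypotheses presented in Section 6.2".

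SAP 6.2 then describes a procedure for the key secondary efficacy analyses, "using a fixed sequence testing procedure to control the overall level of significance". After the primary non-inferiority test it lists three steps: "Superiority analysis of the time to loss of Secondary Patency", then "Non-inferiority analysis of the time to loss of Primary Patency", then superiority on Primary Patency. There is no infection hypothesis in the list.

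Infection carries the same rank as Primary Patency. SAP 2.2.0.3 lists it as the "Key Secondary Safety Endpoint", and the protocol's key secondary objectives (3.2.1) include "To compare the rate of access-related infections for the HAV with that of the ePTFE graft".

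Its analysis appears in the Access-Related Infections part of SAP 7.2 and in protocol 10.4. Two rates per 100 person-years are defined: one over conduit use, censored at abandonment, and one over the 2-year follow-up. The SAP says: "The analysis will be conducted using a two-sided test at the alpha=0.05 level of significance". Protocol 10.4 makes clear that the comparison is made for each of the two definitions, so there are two tests.

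**The concern.** Read literally, SAP 4 and 4.5 promise error control for every key secondary endpoint, and the plan supplies none for infection. Its two tests do not depend on the patency results, the 0.05 is not split between them, and neither is named as the main one.

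This matters because infection is not treated as routine safety monitoring. Protocol 2.4.3.1 and 2.5.2 name fewer infections among the potential advantages of the HAV, and protocol 10.4 makes infection the only safety outcome with inferential statistics. A significant result on either rate could be presented as a controlled key secondary finding, even if the primary analysis failed.

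**Working it through.** **1. The passages compared.**

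| Item | Labelled key secondary? | In the 6.2 sequence? | Alpha |
|---|---|---|---|
| Secondary Patency, superiority | Key secondary analysis of the primary endpoint | Yes, step 1 | 0.05, if all earlier tests succeed |
| Primary Patency, non-inferiority then superiority | Yes | Yes, steps 2 and 3 | 0.05, if all earlier tests succeed |
| Infection, conduit-use rate | Yes | No | 0.05, unconditional |
| Infection, 2-year rate | Yes | No | 0.05, unconditional |

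**2. The plan's own figure.** In a fixed sequence run at full alpha, a false positive requires rejection of the first true null reached, so the familywise error is at most 0.05. A simulation with both non-inferiority steps passing and both superiority nulls true gave 0.050. The stated 0.05 is reproduced for the listed patency tests.

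**3. Two infection tests at 0.05 each.**
- Upper bound: 0.05 + 0.05 = 0.10.
- Independent tests: 1 − 0.95² = 0.0975.
- Identical tests: 0.05.
- In between, because the two rates share the infections on the conduit, P(|Z1| > 1.96 or |Z2| > 1.96) for bivariate normal statistics is 0.091 at correlation 0.5, 0.078 at 0.8, 0.071 at 0.9 and 0.065 at 0.95. These correlations are assumptions.

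**4. Assumed infection rates in place of assumed correlations.** The documents give no infection rates. The inputs were 175 per arm (SAP 3.1) and 12-month Secondary Patency of 60% (the ePTFE figure in SAP 11) or, as an assumption, 80%. Also assumed were 20% dropout per year, gamma frailty and a robust-variance rate ratio standing in for the planned Poisson or negative binomial model. There were 4000 trials per setting. Rates are infections per person-year on the conduit / after abandonment.

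| Assumed rates | Either test significant, no true difference |
|---|---|
| 0.10/0.30 or 0.15/0.40 | 9.4-9.7% (60% patency); 8.1-8.3% (80%) |
| 0.12/0.12 | 7.0-7.2% |
| 0.12/0.06 | about 6.6% |
| 0.12/0.02 | about 6.0% |

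The Monte Carlo standard error near 9% is √(0.09 × 0.91 / 4000) ≈ 0.45 percentage points, so about 6-10% is as fine as the result should be stated. The more infection occurs after abandonment, the further the two rates diverge and the higher the figure.

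**5. Direction.** These are two-sided errors. A false finding of fewer infections with the HAV is about half of each: 0.039 at correlation 0.8 and 0.035 at 0.9, against 0.025 for a single test.

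**6. All tests together.** If infection is independent of patency and the sequence spends its full 0.05 on a true null, the error over the primary and all key secondary tests is 1 − 0.95 × (1 − f), where f is the infection figure. With f = 0.078 this is 1 − 0.95 × 0.922 = 0.124. It runs from 0.0975 (f = 0.05) to 0.143 (f = 0.0975), with an upper bound of 0.15. That is the quantity the unrestricted sentence in SAP 4 implies is 0.05.

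**The case against.** The strongest reply is that the operative text already limits the hierarchy to efficacy. SAP 4.5 makes no free-standing promise; it points to 6.2, which opens with key secondary efficacy analyses and lists only patency. Protocol 10.3.3 is headed the same way. Infection sits in the safety analysis, in the safety population rather than ITT, with its own test. On this view a word is missing from two summary sentences, and safety endpoints are often tested without familywise control.

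Much of this stands. Leaving infection outside the sequence may be deliberate, and it is a legitimate choice. Reporting two prespecified rates is also defensible: one describes risk while the conduit is in use, the other the whole 2 years. A reader might infer that the sponsor planned to choose the better of the two, or that the documents somewhere present infection as part of the sequence. Neither is supported: both rates are fixed in advance, and anyone who follows the cross-reference sees that infection is absent.

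The reply does not rescue the two sentences. If the exclusion is intended, SAP 4 and 4.5 claim more than the plan provides. The protocol's statement that secondary superiority comparisons are unadjusted does not settle it. It sits in the additional efficacy analyses (10.3.4), the synopsis words it for efficacy only, and nothing in protocol 10.4 or the SAP infection text marks those p-values as nominal.

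**Conclusion.** The concern holds as a misstatement of scope. SAP 4 and 4.5 describe control that does not reach the key secondary safety endpoint, whatever the correlation between its two tests. The size, about 6-10% for at least one significant infection test under no difference, rests on assumed infection rates, dropout and frailty; only the limits of 5% and 10% are free of those assumptions.

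Two stronger readings should be resisted. A reader might infer that the patency conclusions are compromised; they are not, since the infection tests take nothing from the sequence. A reader might also infer that infection must be the last step of the sequence, using the conduit-use rate. The documents do not settle that. Placed last, infection could be confirmatory only after superiority on both Secondary and Primary Patency. Protocol 2.1 and 2.4.3.2 also say that infection can lead to graft removal or failure, so censoring at abandonment may be informative.

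**What to change.** - In SAP 4 and 4.5, change the scope to *primary and key secondary efficacy endpoints*.
- In the Access-Related Infections section, state that both infection p-values are nominal, are not multiplicity-controlled and cannot support a confirmatory claim.

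If the sponsor wants a confirmatory infection claim, it should do the following before the database lock for that analysis:
- Name one rate as the main test and report the other as supportive.
- State the analysis set, because the sequence uses ITT and infection uses the safety set.
- State the place in the testing order, and the timing if the 2-year rate is chosen, because the sequence runs at 18 months.

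Which rate and which place is the sponsor's choice. As an illustration, a single infection test appended after the last patency step leaves the overall error at 0.05 (simulated 0.050). One test left outside with its own 0.05 gives 1 − 0.95² = 0.0975 across the two families if they are independent.

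The minimum change costs only wording, and the infection result is then described as nominal. The confirmatory route alters a protocol-specified analysis, and if infection joins the sequence its claim depends on the earlier steps. Tests placed ahead of it lose nothing.

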#### **4.1 DATA AND PROGRAMMING QUALITY ASSURANCE**

See Data Management Plan (DMP) for details on monitoring and source data verification.

Once all the source verification is complete, all queries are resolved, and the database has been updated appropriately, the database will be (hard or soft) locked and made available to CTI Biostatistics for analysis. Data may be pulled by CTI Biostatistics for DMC analyses at a time when source verification and query resolution is ongoing and the database is not locked. The DMC analyses may be performed by the CTI study statistician, but the results will not be disclosed to the sponsor.

All SAS programs used to create analysis datasets and output will be validated by ensuring that the “.log” files are void of all errors, warnings and notes indicative of problems. Additionally, each program will be checked to ensure that it performs according to the program specification.

All programs are developed and validated by different members of the CTI Biostatistics Department.

When performing a quality control (QC) review of listings and tables output from SAS, it is not always possible to perform a 100% QC review of all fields. If a 100% QC review is not to be performed, the sample size of fields to undergo QC review may be determined by utilizing American National Standards Institute (ANSI) sampling procedures. Sampling procedures are conducted using “normal” inspection criteria (Inspection Level II, Single, and Normal) and an Acceptable Quality Level (AQL) of 0.010%. The following shows the sampling criteria:

